8.3 Study Visit 2 – 4 weeks post-de-bond (+ / - 3 days)

Preparation of the Calcivis System

The Calcivis System must be prepared according to the manufacturer's Instructions For Use. Single-use Disclosing Solution (Photoprotein) should not be drawn up in to the syringe more than 2 hours before

the first tooth is imaged. Once reconstituted, the multi-use vial of Disclosing Solution (Photoprotein) should be stored at 2 to 8⁰ C, up to a maximum of 2 weeks.

Teeth Preparation Procedures

All teeth found to be active at Visit 1, will be cleaned by the Orthodontist, by brushing with water, and rinsing with water and an air-water spray from a conventional dental 3-in-1 device, according to the Tooth Cleaning Protocol (Appendix 2). Patients will be asked to rinse out thoroughly with tap water. Each free smooth surface will be air dried before being coded for ICDAS (0, 1, 2 or 3).

Close-up digital photographs will be taken of the selected teeth for reference (as per routine orthodontic procedures).

Imaging with the Calcivis device

Extreme care must be taken to ensure the surface of the tooth and surrounding area are free from saliva before imaging with the Calcivis System by air drying for a minimum of 10 seconds immediately before application of the disclosing solution and Calcivis System imaging.

Images of the free smooth tooth surfaces, will be taken with the Calcivis System according to the Instructions For Use. If the first image of a selected tooth is not clear, it is acceptable to take a second image of the selected tooth, however patients must rinse out with water before the subsequent image can be taken, and the tooth air-dried as described above. A maximum of – four images per patient can be taken with the Calcivis System.

Immediately after all imaging has been completed, patients will be asked to rinse out with tap water.

Any adverse events observed or volunteered by the patient will be recorded.

At the end of the imaging procedures, the Investigator will review the images on the laptop and record any “activity” as a YES or NO, according to areas of elevated bioluminescence

The Investigator will share the images of the teeth with the patient at the end of the Visit.

Patients will be advised to follow a routine tooth brushing / oral hygiene regime of brushing teeth at least twice per day with a fluoride toothpaste, taking care to brush any areas highlighted by the orthodontist, and to use a mouthwash at different times of the day from brushing.

The Calcivis System will be dismantled and cleaned according to the Instructions For Use and all consumables will be disposed according to the Instructions For Use.

Visit 2 is then complete.

8.4 Study Visit 3 – 8 weeks post-de-bond (+ /- 5 days) – final study visit

Preparation of the Calcivis System

The Calcivis System must be prepared according to the manufacturer’s Instructions For Use. Single-use Disclosing Solution (Photoprotein) should not be drawn up in to the syringe more than 2 hours before

the first tooth is imaged. Once reconstituted, the multi-use vial of Disclosing Solution (Photoprotein) should be stored at 2 to 8^o C, up to a maximum of 2 weeks.

Teeth Preparation Procedures

All teeth found to be active at Visit 1, will be cleaned by the Orthodontist, by brushing with water, and rinsing with water and an air-water spray from a conventional dental 3-in-1 device, according to the Tooth Cleaning Protocol (Appendix 2). Patients will be asked to rinse out thoroughly with tap water. Each free smooth surface will be air dried before taking close-up colour photographs of the tooth or teeth with a digital camera for reference, and coded for ICDAS (0, 1, 2 or 3). Imaging with the Calcivis device

Extreme care must be taken to ensure the surface of the tooth and surrounding area are free from saliva before imaging with the Calcivis System by air drying for a minimum of 10 seconds immediately before application of the disclosing solution and Calcivis System imaging.

Images of the free smooth tooth surfaces, will be taken with the Calcivis System according the Instructions For Use. If the first image of a selected tooth is not clear, it is acceptable to take a second image of the selected tooth, however patients must rinse out with water before the subsequent image can be taken, and the tooth air-dried as described above. A maximum of four images per patient can be taken with the Calcivis System.

Immediately after all imaging has been completed, patients will be asked to rinse out with tap water.

Any adverse events observed or volunteered by the patient will be recorded.

At the end of the imaging procedures, the Investigator will review the images on the laptop and record any "activity" as a YES or NO, according to areas of elevated bioluminescence

The Investigator will share the images of the teeth with the patient at the end of the Visit.

Patients will be advised to follow a routine tooth brushing / oral hygiene regime of brushing teeth at least twice per day with a fluoride toothpaste, taking care to brush any areas highlighted by the orthodontist, and to use a mouthwash at different times of the day from brushing.

The Calcivis System will be dismantled and cleaned according to the Instructions For Use and all consumables will be disposed according to the Instructions For Use.

Post-Imaging Questionnaires

At the end of the imaging procedures, patients will be asked to remain at the Orthodontic clinic to complete a Patient Questionnaire. Visit 3 is then complete.

In addition, at the end of each final study visit, the Investigator and Dental Nurse will each complete relevant sections of a User-Questionnaire.

Anonymised images from the study patients may be reviewed at a later date by representatives of the Sponsor for publications, educational and / or promotional use. Consent will be sought from the patient and / or parent or guardian.

8.7 Future Dental Care

Depending on the results, the Investigator may provide caries preventive advice to the patient and / or parent or guardian. The Investigator will not suggest further dental treatment based on the result of the images alone.

9. ADVERSE EVENTS

9.1 Definitions

Adverse Event (AE) – any untoward medical occurrence, unintended disease or injury, or untoward clinical signs (including abnormal laboratory findings) in subjects, users or other persons, whether or not related to the investigational medical device.

This definition includes events related to the investigational device and comparator and events related to the procedures involved.

For users or other persons, this definition is restricted to events related to the investigational medical devices.

A Serious Adverse Event (SAE) – is an adverse event that –

- Led to death
- Led to a serious deterioration in the health of a subject that –
 - resulted in a life-threatening illness or injury
 - resulted in a permanent impairment of a body structure or a body function
 - required in-patient hospitalization or prolongation of existing hospitalization
 - resulted in medical or surgical intervention to prevent a permanent impairment of a body structure or a body function
- Led to foetal distress, foetal death or a congenital abnormality or birth defect

Planned hospitalisation for a pre-existing condition, or a procedure required by the CIP, without serious deterioration in health, is not considered a serious adverse event

Adverse Device Effect (ADE) – an adverse event related to the use of an investigational medical device.

This definition includes any events resulting from insufficient or inadequate instructions for use, deployment, implantation, installation, or operation, or any malfunction of the investigational device.

This definition also includes any event resulting from user error or from intentional misuse of the investigational device.

Serious Adverse Device Effect (SADE) – adverse device effect that has resulted in any of the consequences characteristic of a serious adverse event.

Anticipated Serious Adverse Device Effect (ASADE) - an effect which by its nature, incidence, severity or outcome has been identified in the risk analysis report

Unanticipated Serious Adverse Device Effect (USADE) - serious adverse device effect which by its nature, incidence, severity or outcome has not been identified in the current version of the risk report.

Device Deficiency – inadequacy of a medical device with respect to its identity, quality, durability, reliability, safety or performance.

Device deficiencies include malfunctions, use errors and inadequate labelling.

Device deficiencies which result in SAEs or USAEs, will be managed as detailed below.

Device deficiencies that did not lead to an adverse event, but could have led to a medical occurrence if suitable action had not been taken, or intervention had not been made or if circumstances had been less fortunate will also be managed as detailed below.

Use error – act or omission of an act that results in a different medical device response than intended by the manufacturer or expected by the user.

Use error includes slips, lapses and mistakes.

An unexpected physiological response of the subject does not itself constitute a use error.

Severity Definitions – the following definitions will be used to determine the severity rating for all SAEs

- Mild – awareness of signs or symptoms, that does not interfere with the subject's usual activity, or is transient which resolves without treatment and with no sequelae
- Moderate – a sign or symptom which interferes with the subject's usual activity
- Severe – Incapacity with inability to do work or usual activities

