4.2 Secondary Objectives

Secondary Objectives

To assess the safety of the Calcivis System –

this will be measured by the collection of all adverse events.

To assess the value of feedback and/or communication with patients after using the Calcivis System –

this will be measured by Questionnaires for both the Patient and the User

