In May 2014, the first formal Post-Approval Clinical Study was performed in adults (16 to 25 yrs old) using the advanced prototype Calcivis System. The Primary Objectives of the study were to assess the Performance and Safety of the Calcivis System, and the Secondary Objective was to assess user experience with the Calcivis System (both User and Patient). A total of 42 patients were recruited to the study from three UK, General Dental Practices, to obtain a total of 31 evaluable patients. Eligible patients were those with interpretable images of both a tooth with no visible lesion identified (ICDAS Code 0) and a tooth with a suspected visible lesion identified (ICDAS Code 1, 2 or 3). Images from 11 patients were not eligible for interpretation due to confounding factors including ambient light ingress, gross saliva contamination and poor disclosing solution coverage on the tooth surface. All these issues have been addressed in the design phase for the new commercial Calcivis System which is the subject of this study.

All 42 patients were included in the Safety Population – two adverse events were recorded – bleeding gums and slight gum abrasion – both were device-related, non-serious and asymptomatic to the patients with no action required. One other adverse event was recorded as a device deficiency when the device jammed and did not dispense fluid.

31 patients were included in the Agreement Population – analysis of the level of agreement between the ICDAS scores and elevated luminescence, (Y/N) as defined by the Investigators.

For the primary study objectives, the study results concluded that: -

1. The Calcivis System was safe in clinical use as determined by the low number and minor nature of the adverse events recorded.
2. Analysis of the overall level of agreement between elevated luminescence and the presence of lesions predicated as active by the Investigators showed agreement in 47 of the 65 teeth imaged (72.3 %) which was statistically significant, not due to chance and above the expected level of 70%.

(Of the 31 teeth identified by the Investigators with no visible lesions, 26 showed no elevated luminescence using the Calcivis System – corresponding to a negative percentage agreement of 83.9%. Of the 34 teeth with visible lesions identified by the Investigators, 21 showed elevated luminescence using the Calcivis System – corresponding to a positive percentage agreement of 61.8%).

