9.2 Collection and Reporting of Adverse Events

It is the responsibility of the Investigator at the site to ensure that all adverse events (AEs, SAEs, ADEs, SADEs (ASADEs and USAEs) and device deficiencies) occurring during the course of the study are recorded on the Adverse Event Form. Details recorded should include the following information:

- A description of the event
- The dates of the onset and resolution
- Any action taken
- The outcome
- The relationship to the device
- Whether or not the adverse event is serious
- Whether the adverse events arises from insufficiencies in the IFU
- Whether the adverse event arises from user error

Adverse events can be observed directly by the site Investigator or staff, or can be spontaneously reported by the patient. In addition each patient should be questioned about adverse events at each study visit. In all cases it is the responsibility of the site Investigator to collect the information and record as outlined above. All adverse events should be followed up for the duration of the study.

In the case of SAEs, SADEs (ASADEs and USAEs) – including those resulting from device deficiencies, these must be reported to the study Sponsor and to the relevant Ethics Committee according to the term of approval and in addition, any local adverse event reporting guidelines should be followed.

Anticipated Adverse Events are as follows:

- Infection due to cross-contamination from other patient
- Irritation / erythema due to reaction to Disclosing Solution
- Hypersensitivity to the Disclosing Solution
- Pain or discomfort due to presence of intra-oral imaging device in mouth
- Damage / trauma to soft tissue due to presence of intra-oral imaging device in mouth
- Choking hazard from patient biting down on Applicator

Serious Adverse Events, Serious Adverse Device Effects and Unanticipated Adverse Device Effects must be reported to the Sponsor, within 24 hours of becoming aware of the event. In addition a written report is to be provided by the Investigator within 5 working days.

SAEs, SADEs and UDAEs should be sent by email within the specified timelines to:

[contact] and [contact]

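### Section 9.1 limits the mild/moderate/severe scale to SAEs, which its mild grade hardly fits, and the section 9.2 list of details to record omits severity

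*Protocol*

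**What the plan says.** The protocol deals with severity in one place. Section 9.1 (Severity Definitions) states that "the following definitions will be used to determine the severity rating for all SAEs", and then defines three grades. Mild is "awareness of signs or symptoms, that does not interfere with the subject's usual activity, or is transient which resolves without treatment and with no sequelae". The second grade, moderate, turns on interference with usual activity, and severe on incapacity.

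Section 9.2 requires that all adverse events, adverse device effects, their serious forms and device deficiencies "occurring during the course of the study are recorded on the Adverse Event Form". It continues: "Details recorded should include the following information", and lists eight items:

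1. description
2. onset and resolution dates
3. action taken
4. outcome
5. relationship to the device
6. seriousness ("Whether or not the adverse event is serious")
7. whether the event arises from shortcomings in the instructions for use
8. whether it arises from user error

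The anticipated events in the same section include "Pain or discomfort due to presence of intra-oral imaging device in mouth", as well as irritation, soft-tissue damage, infection, hypersensitivity and choking.

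Safety is a secondary objective. Section 4.2 says "this will be measured by the collection of all adverse events", and section 10.2 plans a descriptive summary of adverse events.

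**The concern.** The scale and its stated scope do not match. Three grades that begin with a transient, untreated event suit the general run of adverse events, but the text reserves them for SAEs. Section 9.2 then leaves severity off the list of details to record, so it does not carry through even the rating that 9.1 promises for SAEs.

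The safety statement is at stake. In section 5.7 the sponsor concluded from the earlier study that the device was safe because the events were few and minor. This study would collect the number of events. For the non-serious ones, however, it sets no standard grade on which a claim that they were minor could rest. The intensity of discomfort is a live question for this device: section 5.7 reports one patient in the earlier study who recorded marked pain on the questionnaire.

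**Working it through.** **1. Does the scale fit the events it is assigned to?** Under section 9.1 an SAE led to one of the following: death; life-threatening illness or injury; permanent impairment; in-patient or prolonged hospitalisation; intervention to prevent permanent impairment; or foetal harm. Set against the mild grade, hardly any such event leaves usual activity undisturbed or passes without treatment or sequelae. The lowest grade would be nearly empty if only SAEs were rated. This suggests that 'SAEs' is a slip for 'AEs'.

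**2. Does another section widen the scope?** Sections 4.2, 5.7, 9.2 and 10.2 were checked, and none applies the scale to non-serious adverse events or device effects.

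**3. Does the list in 9.2 supply the rating?** None of the eight items is severity. The seriousness item is a yes/no classification by consequence and not a grade of intensity. Sections 9.1 and 9.2 therefore disagree even for SAEs: one says they will be rated, and the other does not list the rating. Section 9.1 also names severity among the attributes that separate anticipated from unanticipated serious device effects, which again presupposes that it is recorded.

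**4. How many events might this touch?** The protocol gives no figure on this point, so there is none to reproduce. The following is an illustration.

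Inputs:
- Section 5.7: 2 adverse events in 42 patients. The protocol says that "both were device-related, non-serious and asymptomatic to the patients with no action required". One further report, a jammed device, was classed as a device deficiency and is left out.
- Section 10.1: up to 100 patients imaged, to obtain 45 with active lesions.

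Assumptions: the same rate with the commercial device, and at most one event per patient.

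- Rate: 2/42 = 0.0476, or 4.8%.
- Exact (Clopper-Pearson) 95% limits: the lower is the 2.5% point of Beta(2, 41) = 0.0058, and the upper is the 97.5% point of Beta(3, 40) = 0.1616. The interval is 0.6% to 16.2%.
- No serious event in 42: the upper limit of the exact 95% interval is 8.4%.

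| Patients imaged (n) | Expected events (n × 2/42) | Range from the 95% limits | P(at least one) = 1 − (40/42)^n |
|---|---|---|---|
| 100 | 4.8 | 0.6 to 16.2 | 0.992 |
| 45 | 2.1 | 0.3 to 7.3 | 0.889 |

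The last column uses the point estimate of the rate. If these events were non-serious, as both were in the earlier study, the scale as worded would cover none of them.

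**The case against.** The strongest reply is that this is a slip of wording with little consequence. If 'SAEs' was meant to read 'AEs', the Adverse Event Form may already ask for a grade for every event. That is possible, and four stronger readings that a reader might draw go beyond the documents:

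- *The form has no severity field.* The form is not in the document, and section 9.2 introduces its list in terms that make it a minimum. Only the list can be said to omit severity.
- *Non-serious events will go ungraded.* The protocol does not require a grade, but it does not forbid one.
- *A severity table would be empty.* Section 10.2 plans no such table. Any breakdown by severity would be a matter for the SAP.
- *The report could not call any event mild.* The description, dates, action and outcome cover much of the mild definition: whether the event was transient, untreated and without sequelae. What they need not show is interference with usual activity, which is what separates mild from moderate. The Patient Questionnaire at Visits 1 and 3 may add something on discomfort, but its content is not shown.

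The event count is also soft. It carries over the rate of an advanced prototype used in general dental practice in patients aged 16 to 25 to a redesigned device in orthodontic patients aged 12 and over. The figure of 100 is an upper estimate. Moreover, some anticipated events, such as infection, hypersensitivity or choking, could be serious and would then fall within the scale.

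These points limit the claim but do not remove it. A probable slip is still the operative rule until it is corrected, and 9.1 and 9.2 disagree on any reading.

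**Conclusion.** The point holds as a mismatch of scope within the protocol. The scale is tied to SAEs although its mild grade describes ordinary adverse events, and the recorded details omit severity even for the SAEs that are to be rated. As written, nothing requires a severity grade for the non-serious events likely to make up most of the safety data. The safety summary would then have no protocol-defined grade behind a statement that events were minor.

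The size is small: roughly 1 to 16 events if 100 patients are imaged, on the assumptions of an unchanged rate and at most one event per patient. This is a minor improvement confined to descriptive safety reporting. The primary objective, the sample size and the 24-hour reporting of serious events are not affected.

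**What to change.** - In section 9.1, change 'all SAEs' in the severity sentence to 'all adverse events'.
- In section 9.2, add severity to the details to be recorded for each event.
- Check that the Adverse Event Form asks for the grade, and add the field if it does not.

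The cost is small but not nil. Section 14.2 requires a written amendment approved by the sponsor, with ethics approval where needed, and section 14.5 specifies three-part paper case report forms, so a new field may mean a reprint. Any events recorded before the amendment takes effect would have to be graded from the details already on the form, and the report should say so.

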9.2 Collection and Reporting of Adverse Events

It is the responsibility of the Investigator at the site to ensure that all adverse events (AEs, SAEs, ADEs, SADEs (ASADEs and USAEs) and device deficiencies) occurring during the course of the study are recorded on the Adverse Event Form. Details recorded should include the following information:

- A description of the event
- The dates of the onset and resolution
- Any action taken
- The outcome
- The relationship to the device
- Whether or not the adverse event is serious
- Whether the adverse events arises from insufficiencies in the IFU
- Whether the adverse event arises from user error

Adverse events can be observed directly by the site Investigator or staff, or can be spontaneously reported by the patient. In addition each patient should be questioned about adverse events at each study visit. In all cases it is the responsibility of the site Investigator to collect the information and record as outlined above. All adverse events should be followed up for the duration of the study.

In the case of SAEs, SADEs (ASADEs and USAEs) – including those resulting from device deficiencies, these must be reported to the study Sponsor and to the relevant Ethics Committee according to the term of approval and in addition, any local adverse event reporting guidelines should be followed.

Anticipated Adverse Events are as follows:

- Infection due to cross-contamination from other patient
- Irritation / erythema due to reaction to Disclosing Solution
- Hypersensitivity to the Disclosing Solution
- Pain or discomfort due to presence of intra-oral imaging device in mouth
- Damage / trauma to soft tissue due to presence of intra-oral imaging device in mouth
- Choking hazard from patient biting down on Applicator

Serious Adverse Events, Serious Adverse Device Effects and Unanticipated Adverse Device Effects must be reported to the Sponsor, within 24 hours of becoming aware of the event. In addition a written report is to be provided by the Investigator within 5 working days.

SAEs, SADEs and UDAEs should be sent by email within the specified timelines to:

[contact] and [contact]

On receipt of any SAE, SADEs and UADEs, Calcivis Ltd will initiate a Safety Panel review within two working days of becoming aware of the adverse event, with Calcivis Management and Medical / Dental advisors, to determine if there is any safety requirement to stop the clinical study. Any such decision will be communicated to the Investigators as soon as reasonably possible.

